1.3 Sample Size

The dose escalation portion of this study is a design with no dose de-escalation. The sequential cohort enrollment characteristics of this design do not allow a fixed computation of sample size. In a previous study with subjects receiving a 400 µg dose radiolabeled at 10 mCi (i.e., twice the maximum dose planned for this study), zero (0) subjects had an Adverse Drug Reaction (ADR). Therefore, it is expected that no subjects will have an ADR in this study and that each cohort will enroll the minimum planned sample size of subjects. With 2 cohorts of 4 subjects and one cohort of up to 6 subjects, it is anticipated that the study will enroll no more than n=14 subjects.

2.0 Data Analysis Considerations

2.1 Types of Analyses

All results will be based on descriptive statistics. Unless otherwise stated, continuous variables will be summarized via sample size, mean, standard deviation, median, minimum, and maximum. Categorical variables will be summarized via frequency counts and percentages.

2.2 Analysis Populations

The following analysis populations will be defined:

Safety: The safety population will include all enrolled subjects who are injected with Tc 99m tilmanocept.

Intent-to-Diagnose (ITD): The ITD population will include all subjects who sign informed consent, who are injected with Tc 99m tilmanocept, and who are imaged.

The analysis of all efficacy endpoints will be conducted on the ITD population. The analysis of all safety and baseline subject characteristics will be conducted on the safety population.

2.2.1 Subgroup Definitions

Analyses may be performed by dose group (Cohort 1, 100 μ g/5mCi; Cohort 2, 100 μ g/10mCi; Cohort 3, 200 μ g/5mCi) and by route of administration (Cohort 3 SC and IV).

2.3 Missing Data Conventions

The analysis of the primary efficacy variables will be carried out on the observed data, i.e., a complete case analysis.

2.4 Interim Analyses

No interim analyses are planned for this study.

2.5 Study Center Considerations in the Data Analysis

A study center is defined as a treatment administration site or group of treatment administration sites under the control and supervision of the same Principal Investigator (PI).

Because this is a single-center study, there will be no selective pooling of study centers in the analysis.

2.6 Documentation and Other Considerations

The data analyses will be conducted using SAS© Software, version 9.4 or later.

3.0 Analysis of Baseline Patient Characteristics

Baseline and demographic characteristics will be summarized by dose group for all subjects in the safety population. Continuous variables will be displayed via summary statistics (mean, median, sample size, standard deviation, minimum, and maximum). Categorical variables will be summarized via counts and percentages.

A detailed listing of demographic data for each subject will also be provided as shown in [Appendix B](#).

4.0 Analysis of Efficacy

4.1 Description of Efficacy Variables

Secondary objectives of the study are to determine the concordance between clinical assessment/diagnosis and the localization of Tc 99m tilmanocept by planar and/or SPECT/CT imaging in cutaneous and non-cutaneous sites of KS; to qualify and quantify Tc 99m tilmanocept localization intensity on imaging with CD 206 locale and quantity by histology and IHC in biopsied KS lesions to determine the optimal IV dose; and concordance of localization of Tc 99m tilmanocept via IV and SC routes of administration by planar and/or SPECT/CT imaging in cutaneous and non-cutaneous sites of KS. The relevant endpoints are the following:

- Per subject localization rate of Tc 99m tilmanocept in at least one KS suspected or confirmed lesion by planar and/or SPECT/CT imaging
- Per lesion/region concordance of Tc 99m localization with anatomical areas of active KS defined by confirmed diagnosis or clinical symptomology

- Localization intensity for each biopsied and clinically defined lesion localized on imaging following IV injection as determined by quantitative SPECT gamma counts
- Per biopsied lesion proportion of CD206-expressing cells and proportion of HHV8-expressing cells as determined by histology and relative IHC fluorescence
- Per lesion/region concordance of IV vs SC Tc 99m localization with anatomical areas of active KS defined by confirmed diagnosis or clinical symptomology.
- Per subject localization rate of Tc 99m tilmanocept in areas other than KS by planar and/or SPECT/CT imaging
- Per area localization rate of Tc 99m tilmanocept in the most frequently identified areas other than KS by planar and/or SPECT/CT imaging

An exploratory objective of the study is to use quantitative Polymerase Chain Reaction (qPCR) methods to measure the amount of Human Herpes Virus 8 (HHV8) present in the biopsy tissue.

The relevant variables are the following:

- Nuclear medicine specialist determination of presence/absence of illumination (i.e., localization positive or negative per anatomic site) relative to background from planar and/or SPECT/CT imaging results for each subject;
- Clinically identified presence or absence of KS based on any previous diagnostic evaluation;
- Proportion of CD206-expressing cells (IHC fluorescence);
- Quantitative SPECT gamma counts for each biopsied lesion localized on imaging following IV injection; and,
- HHV8 concentrations as determined by qPCR for each biopsied lesion.

The calculations and analyses pertaining to each of the variables are shown in Sections 4.2.

4.2 Analysis of Efficacy Variables

Localization in KS Sites

The number and percentage of subjects with at least one biopsy-confirmed or clinically suspected KS lesion that has localized with Tc 99m tilmanocept by planar and/or SPECT/CT imaging will be computed. A 95% exact confidence interval on the per-subject localization rate will be computed. This analysis will be performed by dose group and route of administration.

Per-lesion/region localization of Tc 99m tilmanocept by planar and/or SPECT/CT imaging will be computed across all biopsy-confirmed or clinically suspected KS lesions of all subjects. A 95% exact confidence interval on the per-lesion/region localization will be calculated. This analysis will be performed by dose group and route of administration.

An analysis table will also be provided to display the counts of KS lesions localized by imaging that were not previously identified clinically.

Concordance between IV and SC tilmanocept in biopsy-confirmed or clinically-suspected KS lesion sites will be assessed with a cross-tabulation of the IV and SC findings, including the joint probability distribution. The sampling unit for this analysis will be the site. An exact conditional version of McNemar's test will be performed to test the hypotheses

$$H_0: \pi_{IV} = \pi_{SC}$$
$$H_A: \pi_{IV} \neq \pi_{SC},$$

where π_{IV} and π_{SC} represent the probabilities of localization with IV (only) tilmanocept and SC (only) tilmanocept, respectively. In addition, the number and proportion of subjects with concordance and reverse concordance of observed sites of discrete localization of Tc 99m tilmanocept following IV and SC localization will be summarized.

Localization Intensity by Planar and/or SPECT/CT Imaging

Tc 99m tilmanocept average pixel intensity and percent above background will be summarized with descriptive statistics (mean, standard deviation, minimum, median, maximum, and range) for each biopsied lesion localized on imaging following IV injection of Tc 99m tilmanocept by dose group. Summary statistics will be presented separately by imaging type (planar, SPECT/CT).

Proportion of CD206-expressing Cells

Per biopsied-lesion proportion of CD206-expressing cells as determined by histology and IHC fluorescence will be summarized by descriptive statistics (mean, standard deviation, minimum, median, maximum, and range) by dose group.

Localization in Non-KS Sites

The number and percentage of subjects with at least one anatomical site other than KS that has been localized with Tc 99m tilmanocept by planar and/or SPECT/CT imaging will be computed. A 95% exact confidence interval on the per subject localization rate will be computed. This analysis will be performed by dose group and route of administration.

Locations showing localization of Tc 99m tilmanocept by planar and/or SPECT/CT imaging will be computed across all sites other than biopsy-confirmed or clinically suspected KS sites of all subjects. A 95% exact confidence interval on per location localization will be calculated. (i.e. the rate of localization of each site with respect to the number of subjects). This analysis will be performed by dose group and route of administration.

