Locations showing localization of Tc 99m tilmanocept by planar and/or SPECT/CT imaging that are not locations of biopsy-confirmed or clinically suspected KS sites will be computed across all sites in all subjects. A 95% exact confidence interval on per location localization will be calculated. This analysis will be performed by dose and overall.

Other efficacy analyses will be described in the Statistical Analysis Plan (SAP) for the study.

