1.1.1 Localization Definitions

A localized subject is one for whom Tc 99m tilmanocept by planar and/or SPECT/CT imaging results in the illumination of at least one site relative to background as determined by the nuclear medicine specialist.

A localized KS lesion is a lesion that is both clinically identified or suspected KS (via biopsy-confirmed diagnosis or clinical symptomatology) and is illuminated by planar and/or SPECT/CT imaging.

Localization in areas other than KS will also be defined per subject and per area, where these areas are clinically negative KS locations based on clinical symptomatology.

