All Cohorts Combined	xx	xxx (xxx)	(xxx, xxx)

^a Number of cutaneous and non-cutaneous lesions identified in screening.

Cohort 1 = 100 μ g/5mCi IV; Cohort 2 = 100 μ g/10mCi IV; Cohort 3 = 200 μ g/5mCi IV and SC.

STATKING Clinical Services (DD-MMM-YYYY)

Source Program: xxxxxxx.sas

Page x of y

Table 7. Additional KS Lesions Identified from Imaging That Were Not Seen Clinically - Nuclear
Medicine Findings
Navidea Biopharmaceuticals - Study No. NAV3-24
ITD Population (N=xxx)

Group	Number of Identified Lesions	Number (Proportion) of Subjects with at Least 1 Identified Lesion
Cohort 1 IV	xx	xxx (xxx)
Cohort 2 IV	xx	xxx (xxx)
Cohort 3 IV	xx	xxx (xxx)
Cohort 3 SC	xx	xxx (xxx)
All Cohorts Combined	xx	xxx (xxx)

Cohort 1 = 100 μ g/5mCi IV; Cohort 2 = 100 μ g/10mCi IV; Cohort 3 = 200 μ g/5mCi IV and SC.
STATKING Clinical Services (DD-MMM-YYYY)
Source Program: xxxxxxxx.sas

Table 8. Lesion-level Non-Localization of KS Lesions - Nuclear Medicine Findings
 Navidea Biopharmaceuticals - Study No. NAV3-24
 ITD Population (N=xxx)

Group	Number of Clinically Identified Lesions ^a	Number (Proportion) Not Localized by Imaging	95% Exact One-Sided Binomial CI for Proportion
Cohort 1 IV	xx	xxx (xxx)	(xxx, xxx)
Cohort 2 IV	xx	xxx (xxx)	(xxx, xxx)
Cohort 3 IV	xx	xxx (xxx)	(xxx, xxx)
Cohort 3 SC	xx	xxx (xxx)	(xxx, xxx)
All Cohorts Combined	xx	xxx (xxx)	(xxx, xxx)

^a Number of cutaneous and non-cutaneous lesions identified in screening.
 Cohort 1 = 100 μ g/5mCi IV; Cohort 2 = 100 μ g/10mCi IV; Cohort 3 = 200 μ g/5mCi IV and SC.
 STATKING Clinical Services (DD-MMM-YYYY)
 Source Program: xxxxxxxx.sas

Page x of y

Table 9. Number and Percentage of Concordant and Reverse Concordant Lesions
Navidea Biopharmaceuticals - Study No. NAV3-24
ITD Population (N=xxx)

IV Result	SC Result		Total	Concordance	Reverse Concordance	p-Value (McNemar's Test)
	Localized	Not Localized				
Localized	xx (xxx%)	xx (xxx%)	xx (xxx%)	xxx (xxx%)	xxx (xxx%)	xxx
Not Localized	xx (xxx%)	xx (xxx%)	xx (xxx%)			
Total	xx (xxx%)	xx (xxx%)				

STATKING Clinical Services (DD-MMM-YYYY)
Source Program: xxxxxxxx.sas

Page x of y

Table 10. Summary of Imaging-Localized Biopsied Lesion Localization Intensity by Cohort -
 Imaging = Planar
 Navidea Biopharmaceuticals - Study No. NAV3-24
 ITD Population (N=xxxx)

Group	Variable ^a	Mean	Std Dev	n	Min	Max	Median
Cohort 2 IV	Avg Pixel Intensity Percent Above Background	xx xx	xx xx	xx xx	xx xx	xx xx	xx xx

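### A focus seen only on imaging at a clinically negative site can be reported both as an additional KS lesion (SAP Table 7) and as uptake outside KS (SAP Tables 14 and 15)

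*SAP*

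**What the plan says.** Three rules in the SAP bear on a focus that appears on the scan but was not known clinically.

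- **Definition of a KS lesion.** SAP 1.1.1 states: "A localized KS lesion is a lesion that is both clinically identified or suspected KS". It must also be illuminated on planar or SPECT/CT imaging. Protocol 9.3 has the same definition.
- **Definition of non-KS areas.** The same SAP section defines localization in areas other than KS, "where these areas are clinically negative KS locations based on clinical symptomatology". SAP 4.2 then has a subject-level analysis of "subjects with at least one anatomical site other than KS that has been localized with Tc 99m tilmanocept" (Table 14) and a site-level analysis "computed across all sites other than biopsy-confirmed or clinically suspected KS sites of all subjects" (Table 15). Protocol 9.5.3 uses the same residual rule, for locations "that are not locations of biopsy-confirmed or clinically suspected KS sites will be computed across all sites in all subjects".
- **Imaging-only lesions.** SAP 4.2 also plans a table of "counts of KS lesions localized by imaging that were not previously identified clinically". Its shell, Table 7 in Appendix B, is titled "Additional KS Lesions Identified from Imaging That Were Not Seen Clinically" and gives a lesion count and the proportion of subjects with at least one such lesion.

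Neither document excludes Table 7 foci from Tables 14 and 15, or says how the reader decides that an imaging-only focus is KS. Protocol 7.9 asks the onsite nuclear medicine physician for a technical check and an overall assessment of the scan.

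**The concern.** Table 7 gives the name KS lesion to foci that SAP 1.1.1 does not admit as localized KS lesions. Where such a focus lies at a clinically negative site, the definition of non-KS areas covers it as well. The same observation could then support two opposite statements: that imaging found disease the clinic had missed, and that the tracer localized outside disease.

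The question can arise in practice. Protocol 1.2.1 reports that, in the earlier pilot in KS patients, subcutaneous tracer localized in lymph nodes as well as in KS lesions. Protocol 1.1 says that KS can involve lymph nodes. Cohort 3 receives bilateral subcutaneous injections at the ankle or foot, and Table 7 has a row for that route. An illuminated node could be drainage or disease.

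Two outputs are at stake. Protocol 3.2 says the study will evaluate localization in known and unknown lesions, and Table 7 is the natural table to cite for the unknown ones. Localization outside KS, per subject and per area, is a listed secondary endpoint.

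**Working it through.** **Step 1. Apply each rule to four kinds of focus.** All four are illuminated and none was identified as a lesion at screening.

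| Focus | Table 7 | Tables 14 and 15 |
|---|---|---|
| Clinically negative site, read as KS, not confirmed | Yes | Yes: the site is neither biopsy-confirmed nor clinically suspected |
| Clinically negative site, not read as KS | No | Yes |
| Inside a region already clinically suspected, read as KS | Yes | No: the location is not clinically negative |
| Read as KS and then confirmed by biopsy | Yes | No |

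Only the first row is double-counted. The conflict is real but conditional.

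**Step 2. Ask whether the study data would resolve the first row.**
- Protocol 7.2.3, 7.5.3 and 8.4 provide for one post-imaging biopsy per subject, at a non-visceral site. Its stated purpose is CD206 measurement.
- Footnotes to SAP Data Listings 17 and 19 describe biopsied lesions as already identified clinically.
- SAP 4.1 bases clinical presence or absence of KS on previous diagnostic evaluation, so the scan does not change a site's clinical status.

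Visceral imaging-only foci thus get no study biopsy, and at most one non-visceral focus per subject could be verified.

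**Step 3. Show what one double-counted subject does to Table 14.** The plan's own figure reproduces: cohorts of 4, 4 and up to 6 (SAP Table 1) give 4 + 4 + 6 = 14. The documents give no expected number of imaging-only foci, so what follows is an illustration. It assumes one subject whose only uptake outside known KS is one disputed focus, and no other subject in the group with non-KS uptake. As written, Table 14 shows 1/n. If the focus is assigned to Table 7 alone, it shows 0/n.

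The exact (Clopper-Pearson) upper limit for x of n is the 1 − a quantile of Beta(x + 1, n − x), with a = 0.025 two-sided and a = 0.05 one-sided. At x = 0 it equals 1 − a^(1/n); for n = 4, 1 − 0.025^(1/4) = 60.2%. Both versions are shown because SAP 4.2 does not state the sidedness and the table shells specify one-sided.

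| n | Rate: as written → exclusive | Shift (points) | Two-sided upper limit | One-sided upper limit |
|---|---|---|---|---|
| 4 | 1/4 = 25.0% → 0% | 25.0 | 80.6% → 60.2% | 75.1% → 52.7% |
| 6 | 1/6 = 16.7% → 0% | 16.7 | 64.1% → 45.9% | 58.2% → 39.3% |
| 14 | 1/14 = 7.1% → 0% | 7.1 | 33.9% → 23.2% | 29.7% → 19.3% |

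**Step 4. Table 15.** SAP 4.2 sets its denominator as the number of subjects, site by site. Reassigning one focus moves that site's row by the same 1/n, even if the subject has uptake at other non-KS sites, provided it was the only focus counted for that subject at that site.

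**The case against.** The strongest objection is that the tables use different tests and units. Table 7 counts lesions not previously identified; Tables 14 and 15 concern anatomical sites that are clinically negative. A lesion missed at screening in a KS-positive region enters only Table 7. This is plausible: for subjects with 50 or more lesions, the form in Protocol Appendix 5 counts lesions in only three chosen regions. Subjects in inclusion category 4c may have suspected non-cutaneous KS, so a visceral focus at the suspected site is also outside Tables 14 and 15. This stands. A reader might infer that every imaging-only focus is by definition a non-KS focus, and the documents do not support that.

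A second objection concerns the evidence. A reader might cite kidney and bladder accumulation as a source of double counting. Protocol 1.3.1 reports it from a nonclinical distribution study, and nothing suggests that a nuclear medicine physician would call such activity KS. It would belong in Tables 14 and 15 only. The lymph-node finding is the relevant human evidence.

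A third is that, if physiologic uptake is common, Table 14 will be near its ceiling whatever happens to the disputed foci. This also stands: the shifts in Table 14 require a subject with no other non-KS uptake. The effect is more likely to show in Table 15.

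Finally, Table 7 matches no listed secondary endpoint, carries no interval or test, and says in its title that the lesions were not seen clinically. Data Listing 18 records whether each lesion was identified clinically or by imaging. That keeps the foci traceable, but it is not a rule assigning them to a table, and the title still calls them KS.

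**Conclusion.** The point holds as a conflict between stated rules. Followed as written, the SAP can report one unverified focus both as an additional KS lesion and as non-KS uptake. This is limited to foci at clinically negative sites that the reader calls KS and that no biopsy confirms.

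Its size cannot be computed from the documents. The shifts of 25.0, 16.7 and 7.1 points show the leverage of one subject under the stated assumptions and are not forecasts. A reader might picture the extreme in which one imaging-only node in each of 14 subjects gives 14/14 in both Table 7 and Table 14. That case can be constructed, but nothing in the documents makes it expected. Nor do they plan a formal claim of occult KS detection from Table 7.

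The analyses concerned are secondary or supplementary, and the primary ADR endpoint is untouched. The change should be made before images are read, because a rule chosen afterwards could follow the results.

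**What to change.** - Retitle Table 7 *Imaging-only foci read as suspected KS, KS status not verified*, and show separately any confirmed by biopsy or by an existing diagnostic test.
- State in SAP 1.1.1 and 4.2 that each imaging-only focus is counted either in Table 7 or in Tables 14 and 15, never both. Write down the assignment rule and fix it before image reading.
- Carry the matching exclusion into the shells of Tables 14 and 15. Because Protocol 9.5.3 uses the same residual rule as the SAP, record the exclusion as a clarification of that section.

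The cost is edits to three table shells (7, 14 and 15) and one added classification field for the existing reader, since Data Listing 18 now has only the source of identification and the visualization result. Table 7 will look less favourable. A footnote on unverified status would be cheaper, but would leave the double count in place. No additional biopsy or imaging is needed.
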